The principal investigator and designated staff must record the reason for the subject's withdrawal on the case report forms, specifically in the Early Termination Visit and /or a Note to File Form.

Study participants discontinued from the clinical trial who received at least one infusion (HB-adMSCs or placebo) will be invited to a Safety Follow-up visit approximately 30 days after that single infusion.

Any withdrawal must be documented in the source documents and electronic case report forms. If the reason for the discontinuation is an adverse event or serious adverse event, the event must be followed until resolution by the principal investigator.

The Sponsor may temporarily or permanently discontinue the clinical trial at any time for safety, ethical, compliance or other reasons. Study's principal investigator and regulatory authorities will be notified about this decision and the reason of it.

Selection of Clinical Trial Population

Clinical Trial Population

This clinical trial is designed to include adult male and female outpatients with Relapsing Remitting Multiple Sclerosis. Study participants who fulfil all the inclusion criteria and none of the exclusion criteria are eligible for participation in the clinical trial. See below eligibility criteria:

Eligibility Criteria

Inclusion Criteria

A study participant will be eligible for inclusion in this study only if all the following criteria apply:

1. Male and female participants 18 – 75 years of age.
2. Study participants must have been diagnosed with Relapsing Remitting Multiple Sclerosis (RRMS) for at least 6 months before study participation.
3. Study participants must be stabilized on any MS therapy for at least 6 months prior to randomization.
4. Study participants must agree not to increase or begin any Diseases Modifying Therapies for MS during participation in the clinical trial.
5. Study participants must have an EDSS score between 3.0 to 6.5. (Patient must be able to walk).
6. Study participants must have previously banked their mesenchymal stem cells with Hope Biosciences.
7. Study participants should be able to read, understand and to provide written consent.
8. Before any clinical-trial-related procedures are performed, informed consent must be obtained from the participants voluntarily.
9. Female study participants should not be pregnant or plan to become pregnant during study participation and for 6 months after last investigational product administration. *

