17. Participants' life expectancy must not have been considerably limited by other comorbidities, a history of previous myelodysplasia, or hematologic illness.

* Acceptable reversible and permanent methods of birth control include:

1. True sexual abstinence (abstaining from sexual activity during the entire period of risk).
2. Surgery (occlusion bilateral tubal ligation, vasectomized partner).
3. Hormonal contraceptives associated with ovulation inhibition (oral, injectable, implantable patch, or intravaginal).
4. Intrauterine device (IUD), or intrauterine hormone-releasing system (IUS).

Recruitment of Study participants

This clinical trial has been created to enroll 24 study participants diagnosed with Relapsing Remitting Multiple Sclerosis. A single site located in Sugar Land; Texas will be used for this clinical trial. Each study participant will undergo a Screening visit, prior to Infusion 1 (Baseline). Each study participant will receive a unique subject identification number which must be entered in the screening log. This screening number will be assigned sequentially in the order in which

the study participants are screened. The result of the screening visit should be recorded in the screening log by the study delegated staff. See figure below with Screening log.

Study Treatment Description

In this clinical investigation, eligible study subjects will be randomized to either HB-adMSCs or placebo. Randomization process will be conducted during screening process by a designated study randomizer. See below the description of the study treatment.

HB-adMSCs Infusions

Study subjects must have banked their mesenchymal stem cells with Hope Biosciences to participate in this clinical trial. Study subjects who are randomly assigned during the screening process to the HB-adMSCs group will receive their own mesenchymal stem cells in each infusion with a dose of 200 million cells.

Study subjects, investigators and study staff will be blinded to the assigned treatment. To maintain the blinding of this investigation, amber plastic bags shall be used to cover treatment bags. Only subject identification number, patient initials, date of birth and the phrase: "Caution: New Drug Limited by Federal law to Investigational Use (required by 21 CFR 312.6) will be on the bag label, to ensure proper distribution.

Placebo Infusions

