Study subjects who are randomly assigned during the screening process to the Placebo group will receive Saline Solution 0.9% in each infusion.

Study subjects, investigators and study staff will be blinded to the assigned treatment. To maintain the blinding of this investigation, amber plastic bags shall be used to cover treatment bags. Only subject identification number, patient initials, date of birth and the phrase: "Caution: New Drug Limited by Federal law to Investigational Use (required by 21 CFR 312.6) will be on the bag label, to ensure proper distribution.

Each study treatment will be provided by Hope Biosciences, LLC after all quality control essays have been performed and the results are within normal range.

Treatment Regimen

Study subjects will receive the allocated treatment (HB-adMSCs or Placebo) through intravenous infusion only, with a treatment duration of 32 weeks, infusion rate 4-5ml/min and total volume of 250 ml Sodium chloride 0.9%. Each study participant will receive a total of 6 doses of HB-adMSCs or Placebo with a dosing regimen of approximately 4 to 8 weeks between infusions.

Study Treatment Storage, Preparation and Administration Instructions.

Each syringe with the study treatment (HB-adMSCs or Placebo) is individually packaged in a Styrofoam cooler with a temperature strip and icepacks. The product should not be stored since it is meant for immediate preparation and infusion. In the event of unanticipated delays, the product should be kept in a refrigerator (2° to 8°C) for a time not to exceed 96 hours. **Do not freeze. Do not use any syringe or other infusion supplies beyond the expiration date.**

The infusion should be prepared by a designated unblinded pharmacist using aseptic technique with the following procedures: (detailed instructions will be available in the Investigational Product Manual):

1. Gather all equipment and materials you need including cooler with HB-adMSCs or placebo.
2. Don non-sterile gloves and clean countertop where infusion is to be prepared using antibacterial wipes according to manufacturing instruction.
3. Remove and discard gloves, clean hands with hand sanitizer and allow to dry.
4. Don non-sterile gloves.
5. Open cooler and remove bag containing syringe with the study treatment.
6. Check the randomization procedure by checking the study subject's identification number and date of birth.

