	<pre> graph TD     subgraph Placebo_Path [Placebo]         direction TB         M[Manufacturer] --- BE[Baxter or an equivalent manufacturer]         BE --- D[20 ml sterile saline]         D --- R[Intravenous]         R --- AR[4-5 ml/min]         AR --- P[Preparation]         P --- PS[Placebo will contain 20 ml of sterile saline. Placebo should be diluted in 250 ml of 0.9% Sodium chloride.]     end      subgraph HBadMSCs_Path [HB-adMSCs (autologous)]         direction TB         H[Hope Biosciences] --- D2[2 x 10^8 ± 20% cells suspended in 20 ml sterile saline]         D2 --- R2[Intravenous]         R2 --- AR2[4-5 ml/min]         AR2 --- P2[Preparation]         P2 --- PS2[Syringe will contain 20 ml of autologous HB-adMSCs. HB-adMSCs should be diluted in 250 ml of 0.9% Sodium chloride.]     end </pre>	
Study Intervention Assignment	
 
Participants will be randomised 1:1 to receive HB-adMSCs active treatment or Placebo.
 
	
Interim Analysis	
 
No interim analysis will be performed in this study
 
	

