## 4. ANALYSIS SETS

Population	Definition / Criteria	Analyses Evaluated
Safety analysis set	

• All randomised subjects who received at least one dose of HB-adMSCs infusion or placebo.

• If participants receive a treatment different to their randomized treatment, they will be analysed according to the treatment actually received.

	

• Safety

• Study Population

Efficacy analysis set	

• All randomized participants who received all 6 infusions of HB-adMSCs or placebo.

• Participants will be analysed according to their randomized treatment.

	

• Efficacy

Screened Population	

• This population consists of all subjects who signed an ICF to participate in the clinical trial.

• This population will be used for summarizing screening failures and reasons for screening failures.

	

• Study Population

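### Eligibility requires only that cells were banked, so a bank found inadequate after randomisation removes participants from the efficacy set in the active arm only

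*Protocol*

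**What the plan says.** **Eligibility.** Protocol, Inclusion Criteria, item 6: "Study participants must have previously banked their mesenchymal stem cells with Hope Biosciences". No other criterion concerns the quality or quantity of the banked cells. Exclusion 6 bars stem cell treatment in the preceding 12 months but exempts cells made by Hope Biosciences, so an eligible candidate may already have used part of a bank.

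**Active product.** Under HB-adMSCs Infusions, participants in that arm "will receive their own mesenchymal stem cells in each infusion with a dose of 200 million cells". SAP section 2.2 specifies 2 × 10^8 ± 20% "cells suspended in 20 ml sterile saline".

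**Placebo.** Participants assigned "to the Placebo group will receive Saline Solution 0.9% in each infusion". SAP section 2.2 gives the source as "Baxter or an equivalent manufacturer".

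**Release.** The protocol says that each study treatment "will be provided by Hope Biosciences, LLC after all quality control essays have been performed and the results are within normal range". The sentence covers both arms.

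**Order of events.** Randomisation follows the investigator's eligibility decision during screening, before infusion 1 (Investigational Plan, Visit 1; Study Treatment Description). No supply check is placed before it.

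**Analysis.** SAP section 4 defines the efficacy analysis set as "All randomized participants who received all 6 infusions of HB-adMSCs or placebo". Section 5.2 uses that set for the primary endpoint.

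**The concern.** All candidates must have a bank, but only those assigned to cells depend on it. If a bank turns out to be unqualified or too small, an active participant misses an infusion and leaves the primary analysis. A placebo participant with an equally poor bank receives saline, completes six infusions and stays. The active group is then selected on the adequacy of each person's own cells and the placebo group is not, so the efficacy set is no longer a fully randomised comparison.

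The direction of any bias is unknown, because the documents do not relate bank adequacy to outcome. With about 12 participants per arm, losing even one to three from one side for a reason tied to the patient is enough to matter.

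**Working it through.** **Nothing to reproduce.** Neither document states a dose-failure rate, an expected number of missed infusions or a dropout allowance. The sample size of 24 comes without inputs. The calculation below is illustrative.

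**Inputs from the documents.** About 12 active participants (24 randomised 1:1), 6 infusions each, so 12 × 6 = 72 active doses. One missed infusion is enough for exclusion (SAP section 4).

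**Assumption.** A proportion f of active doses fails and is not replaced in time, with f from 1% to 5%. Expected placebo loss from an inadequate bank is 0.

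**Independent failures.** P(participant misses at least one of six) = 1 − (1 − f)^6. P(at least one failure among 72 doses) = 1 − (1 − f)^72.

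| f | P(participant affected) | Expected of 12 | P(at least one of 72 fails) |
|---|---|---|---|
| 1% | 1 − 0.99^6 = 5.9% | 0.70 | 51.5% |
| 2% | 1 − 0.98^6 = 11.4% | 1.37 | 76.7% |
| 5% | 1 − 0.95^6 = 26.5% | 3.18 | 97.5% |

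**All six doses share one fate.** If one bank supplies all six doses and they succeed or fail together, P(participant affected) = f. Expected losses are 12 × 0.01 = 0.12, 12 × 0.02 = 0.24 and 12 × 0.05 = 0.60. For a given f, positively correlated failures fall between these figures and the table, so the table is the upper end.

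**Replacement.** If half of the failed doses were replaced in time, f = 5% becomes 2.5%, and 1 − 0.975^6 = 14.1%, or 1.7 of 12.

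**Power is secondary.** For an assumed standardised difference of 1.0 (normal approximation, two-sided 5%), power is 68.8% at 12 v 12, 66.8% at 11 v 12 and 62.1% at 9 v 12. The selective exclusion matters more than the lost precision.

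**Effect of the fix.** Inadequate banks found before randomisation become screen failures and cannot differ by arm, so expected one-sided loss from that cause is 0. Failures of later doses from an adequate bank remain. If efficacy is analysed in all randomised participants, a missed infusion excludes nobody and 12 v 12 is kept at any f, provided the Week 52 assessment is still obtained.

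**The case against.** The strongest reply is that silence in an eligibility line does not show that supply goes unchecked. The manufacturer already holds the cells and may well review them. Exclusions 12 and 16 let the investigator refuse someone unlikely to complete or otherwise unsuitable, and the Investigational Product Manual, which is not available here, may cover failed doses. All of this is possible, but none of it is stated. The two exclusions are general judgement and are not tied to supply, and a preparation manual would not change what inclusion 6 requires.

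Three stronger readings are tempting and are not supported:

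- **That each active participant needs six separately released lots while saline cannot fail.** The documents do not say whether the six doses share one bank or are separate lots. The requirement that supply follows only "after all quality control essays have been performed and the results are within normal range" is written for each study treatment, and both arms use the same syringe, cooler and temperature check. What is one-sided is dependence on the patient's own bank.
- **That every failed dose is a missed infusion.** Visit timing is approximate and the infusion interval is given as roughly 4 to 8 weeks, so a failure may mean only a delay.
- **That product failures would unblind the site.** This happens only if blinded staff or the participant learn the reason. No passage sends release results to them, and treatment records are kept in a binder open only to the unblinded pharmacist. A rescheduled visit alone is a weak cue.

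The protocol's Statistical Methods section also describes a wider analysis, of data from everyone enrolled who received product. That would soften the consequence, but the SAP names the six-infusion set for the primary endpoint.

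**Conclusion.** The point holds as a low-cost improvement. As written, an inadequate bank discovered after randomisation leads to exclusion from the primary analysis in the active arm only. That follows from inclusion 6, the autologous supply and the efficacy set read together.

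Its size is unknown. The range of 6% to 26% of active participants assumes 1% to 5% failures per dose, independence and no replacement. A reader should not take it as an estimate for this trial, nor as what a bank check would prevent, because only the share due to inadequate banks is avoidable that way.

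**What to change.** **Main change.** Amend inclusion 6 so that, before randomisation, the manufacturer confirms from its records, for every candidate and without knowledge of the arm, that the banked cells are qualified and sufficient for the six planned infusions. A candidate without that confirmation is a screen failure. Both arms are then selected in the same way.

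**Cost.** One protocol sentence and a record check for each candidate (at least the 24 to be randomised) by the party that already holds the cells. The downsides are a few more screen failures and a check for people who later receive placebo.

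**With it.** Define the efficacy set as all randomised participants and collect Week 52 outcomes whatever the number of infusions. This deals with later dose failures, which the check cannot remove.

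**Secondary.** Give blinded staff arm-neutral wording for any product-related rescheduling in either arm, and hold the product reason in the unblinded pharmacy records. This must be reconciled with the Withdrawal Criteria section, which requires the reason for withdrawal on the case report form.

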7. Visually confirm temperature tape is in biohazard bag and is within range (2° - 8° C), document compliance.
8. Visually confirm syringe is closed with cap.
9. Remove syringe from bag and begin mixing syringe, gently rocking back and as well as rolling between hands, bringing the study treatment to room temp, and suspending them into a homogenous solution. No particulates should be visible.
10. Inject the contents into a 250cc bag of normal saline for injection
11. Properly label the infusion bag with the subject ID, D.O.B, preparation date, time and expiration and cover it with an amber bag.

Once, the study treatment has been mixed by the unblinded pharmacist following the above procedures, the infusion nurse or designated study staff will administer the study treatment as follows:

1. Confirm that the subject number and DOB placed on the amber bag label belong to the subject receiving the infusion.
2. Administer the infusion solution over a period of 1h (infusion rate 4-5ml/min).
3. Do not store or reuse any unused portion of the infusion solution. Any unused product or waste material should be disposed in a biohazard container.
4. Complete the source documents of the visit to accurately collect the start and end times of the infusion and add comments if necessary.
5. The study's subject will be monitored for a total of 2 hours from drug exposure to discharge.
 - During the Investigational product administration (1 hour) vital signs will be measured at minute 0, 15, 30, 45, and 60.
 - Post infusion, vital signs will be measured at minute 90 and 120.
6. Follow study procedures as described in the schedule of assessments of the visit.

Investigational Product Assignment (Randomization and Blinding)

A total of 24 eligible subjects will be randomized to either placebo (approx. 12) or active drug (approx. 12) (HB-adMSCs) in a 1:1 balanced design. The randomization will be applicable only to eligible subjects. If a subject is not eligible during the screening process for study participation, this subject shall not be randomized to any group.

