9-Hole Peg Test		X		X		X		X	X
Multiple Sclerosis Quality of Life Inventory 54		X		X		X		X	X
Patient Health Questionnaire 9 (PHQ-9)		X							X
Study Treatments Administration		X	X	X	X	X	X		
24 hours Telephone Encounter		X	X	X	X	X	X		
Video Documentation		X				X			X
AE and SAE assessments		X	X	X	X	X	X	X	X

¹ Collection of laboratory samples (CBC, CMP & Coagulation Panel)

Study Visits 1 to 9.

Visit 1 – Screening.

At the Screening Visit (Visit 1), study participants' information will be collected by study's delegated personnel for evaluation of trial eligibility. The following information is required to determine eligibility:

1. Signing Informed Consent Form (prior to any trial-related activities).
2. Collection of demographic information, such as age, race, ethnicity, date of birth, gender, and relevant medical and surgical history.
3. Collection of Medical History and concomitant medications, including relevant information about the past and present health of study participants.
4. Inclusion and Exclusion criteria evaluation.
5. Measurement of vital signs including respiratory rate, body temperature, blood pressure, pulse rate, oxygen saturation, and measurement of weight and height.
6. Collection of laboratory samples, including Comprehensive Metabolic Panel (CMP), Complete Blood Count (CBC), Coagulation Panel, and Urine pregnancy test if female of childbearing potential.
7. Physical examination by Principal Investigator, including clinical assessments such as Expanded Disability Status Scale (EDSS).

Within 28 days of the Visit 1 - Screening, the principal investigator must decide participant's eligibility. Once, the eligibility of the subject has been confirmed by the principal investigator, the randomization process will be conducted.

Visit 2 and 6 – Infusion 1 (Baseline) and Infusion 5

The following procedures are required during this visit:

1. Update medical history and concomitant medications if any change occurred since last visit.
2. Measure vital signs including respiratory rate, body temperature, blood pressure, pulse rate, oxygen saturation and measurement of weight.
3. Collect laboratory samples, including Comprehensive Metabolic Panel (CMP), Complete Blood Count (CBC), Coagulation Panel and Urine pregnancy test if female of childbearing potential.

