4. Physical examination by Principal Investigator, including clinical assessments such as The Barthel Index, 9 Hole Peg Test, Multiple Sclerosis Quality of Life (MSQOL)-54 Instrument and Patient Health Questionnaire (PHQ-9 is only needed during Infusion 1 and EOS).

5. Investigational product administration by delegated study personnel. HB-adMSCs or Placebo should only be administered intravenously, with a dosing rate of 4-5ml/min and a vital sign monitoring of two hours post-drug exposure. Monitoring time may be prolonged if decided by principal investigator. Vital signs must be monitored as follows:
6. A video documenting study participant walking and standing from sitting will be recorded during this visit.
7. Assess the incidence of any adverse event.
8. 24 hours after administration of the investigational product, study participants will be contacted by telephone call to assess the incidence of adverse events.

Visit 3, 5 and 7 – Infusions 2, 4 and 6.

1. Update medical history and concomitant medications if any change occurred since last visit.
2. Measure vital signs including respiratory rate, body temperature, blood pressure, pulse rate, oxygen saturation and measurement of weight.
3. Physical examination by Principal Investigator.
4. Investigational product administration by delegated study personnel: HB-adMSCs or Placebo should only be administered intravenously with a dosing rate of 4-5ml/min and vital sign monitoring of two hours post-drug exposure. Monitoring time may be prolonged if decided by principal investigator. The monitoring of vital signs shall be the same as represented in Figure 8.
5. Assess the incidence of any adverse event.
6. 24 hours after administration of the investigational product, study participants will be contacted by telephone call to assess the incidence of adverse events.

Visit 4 – Infusion 3

1. Update medical history and concomitant medications if any change occurred since last visit.
2. Measure vital signs including respiratory rate, body temperature, blood pressure, pulse rate, oxygen saturation and measurement of weight.
3. Physical examination by Principal Investigator, including clinical assessments such as The Barthel Index, 9 Hole Peg Test and, Multiple Sclerosis Quality of Life (MSQOL)-54 Instrument.

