If an infusion is stopped for a subject due to an adverse event or serious adverse event, including but not limited to hypersensitivity reaction/anaphylaxis, no additional study treatment will be given to the study participant who develops the event. Although, the study participant will not receive the investigational product, he or she must be followed for safety purposes according to the protocol.

Study Stopping Rules

This Clinical Trial will stop if any of the following events are present:

1. Subject's Death.
2. Occurrence of any thromboembolic event during or after HB-adMSCs administrations (up to 72 hours).
3. Any cerebrovascular ischemia or seizure event occurring within 72 hours after any of the investigational product administrations.
4. Any Serious Adverse Events determined to be related to the following:

- When there is one CTCAE.v5 grade 4 or 5 AE, irrespective of attribution.
- Either any CTCAE Grade 2 adverse event that persists for more than two weeks, or any Grade 3 adverse event, that occurs within 72 hours after product administration.

Should the study participant discontinue study treatment he/she will be followed for safety according to the protocol safety monitoring plan. The study participant will receive follow up communication via phone calls and/or electronically to ascertain the outcome until resolved fully. All will be documented as per protocol.

All changes to the study stopping rules shall be reviewed by FDA. If the study is suspended for any reason, it will not be re-opened until FDA agrees. Regardless of whether the study is stopped or suspended all subjects will be followed to the EOS as per protocol.

Statistical Methods

Sample size consists of up to 24 subjects who have been diagnosed with Relapsing Remitting Multiple Sclerosis. All data collected from subjects who are enrolled and received the investigational product will be analyzed. The incidence of Adverse Events and Serious Adverse Events will be recorded and reported. Efficacy will be measured by improvement of subject's signs and symptoms associated with Multiple Sclerosis. Interim analysis of all safety and efficacy data may be performed at any time deemed appropriate by the Sponsor. Although, the subject's data may be analyzed at any time, a data analysis of all available data will be conducted when a least 10 subjects in each group have completed Week 24. Data may be analyzed for internal informational purposes, reports, presentations, and manuscripts.

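### Stopping rules that turn on the 72 hours after an infusion have no scheduled contact after the 24-hour call, so a trigger event between hours 24 and 72 may be learned of only weeks later

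*Protocol*

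**What the plan says.** **Stopping rules (Protocol, Study Stopping Rules).** A single event can stop the trial.

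- Rule 2 covers thromboembolic events during an infusion or up to 72 hours after it.
- Rule 3 covers "Any cerebrovascular ischemia or seizure event occurring within 72 hours after any of the investigational product administrations".
- Rule 4 includes "Either any CTCAE Grade 2 adverse event that persists for more than two weeks, or any Grade 3 adverse event, that occurs within 72 hours" of product administration.
- Two triggers carry no time window: death (rule 1) and, under rule 4, "When there is one CTCAE.v5 grade 4 or 5 AE, irrespective of attribution".
- Rule 4 opens by referring to serious adverse events. It is therefore unclear whether its Grade 2 and Grade 3 criteria reach non-serious events.

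**Scheduled observation after an infusion.**

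- On site, under the administration instructions: "The study's subject will be monitored for a total of 2 hours from drug exposure to discharge".
- By telephone, in the list for each infusion visit: "24 hours after administration of the investigational product, study participants will be contacted by telephone call to assess the incidence of adverse events". Table 4 carries this as a single row, "24 hours Telephone Encounter", marked at the six infusion visits only.
- After that, Table 4 and the visit lists show nothing until the next visit. For infusions 1 to 5 this is the next infusion visit. For infusion 6 it is the Week 42 follow-up, which has no infusion.

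**Order of procedures at infusion visits (Protocol, Study Visits 1 to 9).** The medical history update and physical examination are listed before product administration. The adverse-event assessment is listed after it.

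The SAP describes how adverse events are summarised but does not address the stopping rules or how their triggers are ascertained.

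**The concern.** A stopping rule protects participants only if the trial learns of the trigger soon enough to act. Here the rules look back over 72 hours, while active questioning after discharge ends at 24 hours. An event at hour 48 meets the rule, but nobody is scheduled to ask about it until the next visit. The Grade 2 persistence criterion has the same difficulty, because no contact falls at or shortly after two weeks.

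What is at stake is continued dosing after a stopping condition has been met. This affects the other participants and, after infusions 1 to 5, possibly the same participant. The infusion-visit lists do not clearly close the gap, since they place the adverse-event assessment after administration. List order need not be the order of conduct, and the history update and examination come first, but the text does not require adverse-event review before dosing.

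**Working it through.** **Inputs, all from the protocol**

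- Infusions at Weeks 0, 4, 8, 16, 24 and 32; follow-up at Week 42 (Study Summary, Table 4).
- Stopping window of 72 hours; telephone call at 24 hours.
- 24 participants and 6 infusions each.

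**Step 1: reproduce the plan's own interval.** The differences between successive infusion weeks are 4, 4, 8, 8 and 8. This matches the 4 to 8 weeks stated under Treatment Regimen. From infusion 6 to the next visit is 42 − 32 = 10 weeks.

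**Step 2: part of the window after the last scheduled contact.** 72 − 24 = 48 hours, and 48/72 = 67%. This is a share of clock time, not a probability of missing an event.

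**Step 3: time from the call to the next scheduled contact.** Days = 7 × weeks to next visit − 1.

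| Infusion | Weeks to next visit | Days from call to next visit | If the next visit may move by ±7 days |
|---|---|---|---|
| 1, 2 | 4 | 28 − 1 = 27 | 20 to 34 |
| 3, 4, 5 | 8 | 56 − 1 = 55 | 48 to 62 |
| 6 | 10 | 70 − 1 = 69 | 62 to 76 |

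The last column is conditional. The window row of Table 4 is incomplete in the text available, so it is not clear which visits carry the ±7 days.

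**Step 4: how many infusions are affected.** 24 × 6 = 144 planned infusions. Of these, 24 × 5 = 120 are followed by another infusion visit and 24 by the Week 42 visit.

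**Step 5: do other provisions supply a contact in hours 24 to 72?**

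- Recording of Adverse Events requires questioning at each contact, but none is scheduled there.
- Unscheduled Visits are at the investigator's discretion. The listed reason that bears on this is an adverse event needing follow-up, which must already be known.
- The telephone or electronic follow-up under Study Stopping Rules is for a participant who has discontinued treatment, to follow an outcome.
- Serious-event reporting and review by the medical monitor or DSMB start once the site knows of the event.

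**Step 6: illustration of exposure during one gap.** The documents give no enrolment period, so one has to be assumed. The simulation used uniform enrolment, all 24 participants staying on schedule, and an event after one of infusions 1 to 5 chosen at random. The mean number of infusions, active or placebo, given to the other 23 participants between the call and the next visit was:

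| Assumed enrolment period | Mean infusions to others |
|---|---|
| 4 weeks | 22.2 |
| 13 weeks | 20.6 |
| 26 weeks | 18.0 |
| 52 weeks | 12.7 |

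**The case against.** The strongest reply is that nothing here is a contradiction. The 72 hours define when an event must occur to count, not when it must be detected. An event at hour 48 that is reported later still meets the rule, and the 24-hour call does not claim to close the window. That is correct, so the point concerns ascertainment and not conflicting rules.

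The second reply is that thromboembolism, stroke, seizure and Grade 3 events often come to light unprompted. This stands in part. A reader might infer that the schedule cannot trigger the rules in time, but the documents do not support that. Spontaneous reports are possible. The consent pages, which may tell participants to call, were removed from the text available, and the serious-event reporting table and the safety monitoring plan cited under the stopping rules are not in it either. On the other side, the protocol's own examples of important medical events include a seizure without hospital admission, which would be a rule 3 trigger. A Grade 3 event, or a Grade 2 event that lasts, is also less certain to be volunteered.

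Third, the participant's own next dose is preceded by a history update and an examination, and the investigator may stop an infusion at any time. That lowers the risk for that participant. It does nothing for others dosed in the meantime.

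A reader might also infer that Visits 3 and 4 could be only 14 days apart (day 28 + 7 = 35 and day 56 − 7 = 49), too soon to judge the two-week criterion. That requires ±7 days at every infusion visit, which the table does not clearly show, and opposite extremes at the two visits. It also sits badly with the stated interval of about 4 to 8 weeks. It should not be relied on.

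**Conclusion.** The gap is real and of moderate weight. Rules 2 and 3 and the Grade 3 criterion under rule 4 depend on a 72-hour window, and no scheduled contact covers its last 48 hours. A trigger event in that interval that is not reported unprompted may be learned of only about 27, 55 or 69 days after the call, depending on the infusion. The two-week Grade 2 criterion also has no scheduled contact at the point of judgement.

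Limits on this conclusion:

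- It does not extend to every stopping rule, since death and Grade 4 or 5 events carry no window.
- After infusion 6 the affected participant has finished dosing, so the remaining risk is to others.
- Rules 2 and 3 are enough to carry the point, whatever the reach of rule 4 to non-serious events.
- A reader might want one fixed number of infusions given in the gap. The documents do not support one, and the 13 to 22 above rests on assumed enrolment of 52 down to 4 weeks.
- The day counts assume visits at their nominal weeks.

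**What to change.** Reconcile Table 4 and the infusion-visit text with the Study Stopping Rules, so that scheduled adverse-event ascertainment covers the windows those rules already use. One way is a further adverse-event telephone contact after the 72-hour window closes, made by the staff who make the 24-hour call and added to both Table 4 and the visit lists. The same passages should be reconciled on how the two-week Grade 2 criterion is to be ascertained, and rule 4 should make clear whether it reaches non-serious events.

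The windows, grades, dose and dosing rules are for the sponsor, and no change to them is proposed.

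The cost is a protocol amendment and at most 24 × 6 = 144 short calls, with no new procedure or assessor.
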